10.7.3 Primary Efficacy Variable(s)

Not applicable.

10.7.4 Drug Concentration Measurements

Not applicable.

10.7.5 Pharmacodynamic Assessments

10.7.5.1 Antibody Response

PD blood sampling for antibody response assessments (antibody concentration specific for GBS-NN/GBS-NN2 and antibody concentration specific for AlpCN, RibN, Alp1N and Alp2/3N) will be collected during the study at the time points specified in Table 10.7.1.

Blood samples (20 mL [2x10 mL samples]) will be taken into serum tubes at each time point, processed as described in the Sample Handling Manual.

Aliquots for GBS-NN/GBS-NN2 antibody response assessments will be analysed at Simbec-Orion Laboratory Service using a validated assay according to applicable local SOPs.

Aliquots for AlpCN, RibN, Alp1N and Alp2-3N antibody response assessments will be analysed at a laboratory contracted by MinervaX.

10.7.5.2 Additional Exploratory Assessments

Blood samples for additional exploratory assessments [REDACTED] will be collected during the study at the timepoints specified in Table 10.7.1.

Blood samples (40 mL [4x10 mL samples]) for [REDACTED] assessment will be taken into [REDACTED] at each time point, processed as described in the Sample Handling Manual. [REDACTED] will be shipped to MinervaX's Laboratory, address: ATT: [REDACTED], Immunology Section, Lund University, [name], Sweden for analysis using validated assays according to applicable local SOPs.

Additional exploratory assessments will be reported separately.

10.7.6 Other Assessments

Blood samples for future validation and calibration work will be collected during the study at the time points specified in [Table 10.7.1](#).

Blood samples (60 mL [6x10 mL samples]) will be taken into serum tubes at each time point, processed as described in the Sample Handling Manual.

Serum aliquots for future validation and calibration work will be shipped to MinervaX AB, [name], Sweden.

10.8 Data Quality Assurance

At the time the study is initiated, a representative of the Sponsor will thoroughly review the final protocol and eCRFs with the Principal Investigator and site staff. During the course of the study the Monitor will visit the Clinical Unit regularly to check the completeness of the participants' records (including the volunteer (participant) master files, laboratory and 12-lead ECG print-outs), the accuracy of entries into the eCRFs, the adherence to the final protocol and to ICH GCP E6 (R2) guidelines^[1], the progress of enrolment and also to ensure the storage, handling and accountability of the IMP. The Principal Investigator and key study personnel will be available to assist the Monitor during these visits.

The Principal Investigator will give the Monitor, Auditor(s), the REC, and the MHRA direct access to relevant clinical records to confirm their consistency with the eCRF entries. No information in these records about the identity of the participants will leave Simbec-Orion. The Sponsor will maintain the confidentiality of all participant records, in line with Section 6.10 of the ICH GCP E6 (R2) guidelines^[1].

Study data will be fully documented in the eCRFs and study logbooks. Dated signatures will be given to account for all interventions in the study by research staff.

Source data are all information in original records and certified copies of original records of clinical findings, observations, or other activities in a clinical study necessary for the reconstruction and evaluation of the study. Source data are contained in source documents (original records or certified copies).

For the purposes of this study the source data will be recorded as detailed in Table 10.8.1.

APPROVAL

Table 10.8.1 Summary of Source Documentation Location

| Data | Source Document | | | |
|---|-----------------------|--------------------|-----------------------|---|
| | Volunteer Master File | eCRF ^{1*} | Clinic Source File | Other Study Documentation |
| Evidence of healthy participant status/primary disease condition for entry into clinical study | X | | | |
| Demographic data (e.g., age, year of birth, gender) | X | | | |
| Demographic data (e.g., race, ethnicity, height, weight, and BMI) | | X | | |
| Medical history | X | | | |
| Inclusion and exclusion criteria | | | X | |
| Informed consents ² | | | | X |
| Participant involvement in the clinical study | | X | | |
| Screening number | | | | X (screening log) |
| Participant number | | | | X (enrolment log) |
| AEs | | X | | |
| SAEs | | | | X (SAE form) |
| Pregnancies | | | | X (Pregnancy notification and outcome form) |
| Previous and on-going therapy | X | | | |
| Concomitant medication | | X | | |
| Results of study examinations (e.g., 12-lead ECGs and laboratory safety tests) ³ | | | X | |
| Vital Signs | | X | | |
| Physical Examination ⁴ | | X | | |
| Study visit dates | | X | | |
| Administration of IMP | | X | | |
| Blood PD and Exploratory sample collection times | | X | | |
| Blood safety sample collection times | | | X (test request form) | |
| Urine safety sample collection times (including start and stop times of collection intervals and volumes) | | | X (test request form) | |
| Injection site reaction photograph if needed | | | | X (Photograph) |
| Temperature, Injection Site Reactions, General Reactions, AE and concomitant medication diaries | | | | X (Participant Diary Cards) |
| Evidence for participation and treatment allocation in MVX0002 | X | | | X (MVX0002 enrolment log and randomisation codes) |

¹ In the event staff are unable to enter data directly into the eCRF (e.g., technical/internet issues), data will be entered directly into a back-up paper source workbook at the time of assessment, then transcribed and subsequently QC'd.

² The original ICFs will be maintained in the study officer file during the clinical phase and will then be transferred to the Project Manager for archiving with the Investigator Site File (ISF) at the end of the study.

³ The 12-lead ECG trace and laboratory safety test print-out including medical review will be stored in the Clinic Source File.

⁴ In the eCRF, the date and time of each physical examination will be recorded. Any abnormal findings will be captured on the Medical History form at Screening and as an Adverse Event during clinical conduct.

AE = adverse event, eCRF = electronic case report form, ECG = electrocardiogram, IMP = investigational medicinal product, PD = pharmacodynamic, SAE = serious adverse event

The above table indicates where source data will be recorded but for completeness the following information will also be recorded in the volunteer master file:

- Clinical study code.
- Study visit dates (pre-dose; post-dose).
- IMP administration (date of dose).
- Results of any key safety and efficacy measures from the clinical study that, in the opinion of an Investigator, should be noted.
- Any concomitant medications used to treat the participant during the study that, in the opinion of an Investigator, should be noted.

The data collected in the eCRFs during the study will be subject to quality control checking by clinical staff prior to sign off.

Designated investigator site staff will enter the data required by the protocol into the eCRF using fully validated software that conforms to 21 CFR Part 11 requirements. Staff will not be given access to the eCRF until they have been trained. Automatic validation programs check for data discrepancies and, by generating appropriate error messages, allow the data to be confirmed or corrected before transfer of the data to the Biometrics group. The Investigator must certify that the data entered into the eCRF are complete and accurate.

The study will be subject to an independent audit by the Simbec-Orion Quality Assurance Unit as outlined in Simbec-Orion SOP GRP-QA 002.

Independent clinical quality assurance audits may be performed at any time during or following completion of the study by the Sponsor, or its authorised agents, and Regulatory Authorities and/or the REC.

10.9 Statistical Methods and Determination of Sample Size

10.9.1 Statistical and Analytical Plan

A statistical analysis plan (SAP) will be written by Simbec-Orion and agreed by MinervaX ApS prior to the locking of the database and subsequent reporting of the study data.

10.9.2 Study Variables/Endpoints

Primary Endpoints

- The following endpoints will be evaluated to assess the safety over 12 weeks of a single dose (booster or first dose) of the GBS vaccine (GBS-NN/NN2): local and systemic reactogenicity; AEs; laboratory tests; urinalysis; vital signs; physical examination.

Secondary Endpoints

- The following secondary **safety endpoints** will be evaluated to assess the long-term safety profile of the GBS-NN/NN2 vaccine 6 months following the dose (booster or first dose): the incidence of autoimmune diseases and/or clinically relevant medical events related to the vaccination that occur in the 6-month follow-up period.
- The following secondary immunological endpoints will be evaluated.

- Individual participant antibody concentration specific for GBS-NN and GBS-NN2, in µg/mL, at 0 and 84 days after the dose (booster or first dose).
- Individual participant antibody concentration specific for AlpCN, RibN, Alp1N and Alp2-3N, in µg/mL, at 0, 14, 28, 56, 84 and 182 days after the dose (booster or first dose).

From the endpoints listed above the following will be derived:

- Geometric mean fold increase in antibody concentration, specific for GBS-NN and GBS-NN2, between Day 1 and Day 85.
- Geometric mean fold increase in antibody concentration, specific for AlpCN, RibN, Alp1N and Alp2-3N, between Day 1 and Days 8, 29, 57, 85 and 183.
- Proportion of participants achieving antibody concentrations, specific for AlpCN, RibN, Alp1N and Alp2-3N, above 0.5, 1, 2, 4 µg/mL, 7, 28, 56, 84 and 182 days after receiving the dose (booster or first dose).

The secondary endpoints relating to antibody concentrations specific for AlpCN, RibN, Alp1N and Alp2-3N and all exploratory endpoints will be analysed and reported separately. Full details of the analyses will be documented in a separate plan(s).

The values of these endpoints on Day 85 will be the basis of the primary immunological analysis; this timepoint is anticipated to be the time of delivery after vaccination in a pregnant woman.

10.9.3 Analysis Sets

Safety Set (SAF): All enrolled participants who receive the study vaccine will be included in the Safety Set. This analysis set will be used for baseline and safety summaries as well as for all study listings.

Immunogenicity Set (IG): The subset of participants who will receive the study vaccine with available post-vaccination titres.

Per Protocol Set (PP): All participants included in the IG Set who do not violate the protocol in a way that may invalidate or bias the results.

The immunological analyses will primarily be performed on the IG Set but will also be performed on the PP set if the number of participants in the PP set differs by more than 5% from that of the IG Set.

10.9.4 Description of Statistical Methods

All statistical analysis will be performed using SAS® (the most up to date version will be used and this will be documented in the SAP).

10.9.4.1 Demographic and Background Data

All demographic and background data will be listed, in addition:

Disposition: Participant disposition will be listed with any withdrawals flagged. Frequencies (number and %) of the total number of participants dosed, completed and prematurely discontinued (including reason for discontinuation) from the study will be summarised.

Additionally, the number and percentage of participants within each analysis set will be summarised.

Demographics: Demographic data will be listed. Descriptive statistics (number of participants in the analysis set (N), number of participants with non-missing observations (n), mean, standard deviation (SD), minimum, median and maximum) will be tabulated for the continuous variables age, height, weight and BMI and frequencies (number and %) for the categorical variable race.

Demographic data will be listed and summarised using the Safety Set. Demographic characteristics will be also presented for other analysis sets (immunogenicity and/or per-protocol) if they differ from the Safety Set.

10.9.4.2 Efficacy Data

Not applicable.

10.9.4.3 Safety Data

All safety data will be listed, in addition:

AEs: All AEs will be coded using the Medical Dictionary for Regulatory Activities (MedDRA) dictionary (the most up to date version that is available at the time of database build will be used and will be listed in the Data Management Plan). The MedDRA dictionary will not be updated during the course of the study.

All AEs occurring up to and including Day 85, including those which occurred prior to dose of IMP, will be listed. Only treatment emergent adverse events (TEAEs), i.e., existing conditions that worsen or events that occur during the course of the study after administration of IMP, will be included within the summary tables.

An overall summary of AEs will be produced including the number of TEAEs; the number and % of participants reporting at least 1 TEAE, serious TEAE, TEAE leading to withdrawal from the study; the number and % of participants reporting TEAEs by severity and relationship to IMP.

The number of TEAEs and the number and % of participants reporting at least 1 TEAE will be tabulated by system organ class (SOC) and preferred term. A participant reporting multiple episodes of a particular AE within a treatment period will only contribute 1 count towards the corresponding SOC and preferred term.

The number of TEAEs and the number and % of participants reporting at least 1 TEAE will be tabulated by preferred term and sorted by descending frequency on the total number of participants with that AE. A participant reporting multiple episodes of a particular AE within a treatment period will only contribute 1 count towards the corresponding preferred term.

In addition, the number and % of participants reporting TEAEs will be tabulated by maximum severity and strongest relationship to IMP. For the summary of TEAEs by severity, if a participant has multiple events occurring within the same SOC or preferred term the event with the highest severity will be counted. Similarly, for TEAEs by relationship to IMP, if a participant has multiple events occurring within the same SOC or preferred term, the event with the highest association to IMP will be counted.

Additionally, the above listings and summaries will be presented separately for autoimmune diseases and/or clinically relevant medical events related to the vaccination that occur in the 6-month (182 days) follow-up period, and systemic and local reactogenicity TEAEs (as defined in the SAP) occurring up to and including Day 85.

Physical examination: Physical examination results will be listed.

Laboratory Safety: Biochemistry, haematology, and urinalysis parameters will be listed with any out of normal range values flagged. Laboratory test results which are out of normal range will also be presented separately along with normal reference ranges. Descriptive statistics (N, n, mean, SD, minimum, median and maximum) of absolute and change from baseline (Screening) biochemistry and haematology parameters at each time point up to and including Day 85 will be tabulated.

Vital Signs: Vital signs parameters will be listed with any out of normal range values flagged. Descriptive statistics (N, n, mean, SD, minimum, median and maximum) of absolute and change from baseline (Day 1 pre-dose) values at each time-point will be tabulated.

Injection Site Reactions: A summary of injection site reactions will be produced by visit and category (redness, bruising, induration, itching and pain), including the number and percentage of participants in each category.

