| This is an open label vaccine booster follow-up study. Participants who had received a primary course of GBS-NN/NN2 or placebo in Study MVX0002 will be invited to return to receive a booster dose (or first dose in the case of placebo or vaccine naïve participants) 1 to 5 years after the completion of the primary course of vaccination. All participants will receive a single dose of GBS-NN/NN2 containing 50µg of each fusion protein. |

A minimum of 30 and a maximum of 40 female participants will be recruited, comprised of between 20 and 30 participants who had received previous vaccination with GBS-NN/NN2 in the MVX0002 study and up to 10 participants who had received placebo in the MVX0002 study. If an insufficient number of previous placebo recipient participants return to this study, vaccine naïve participants will be recruited.

The study will include 7 visits (Visit 1: Screening Period, Visits 2-6: Treatment Period and Visit 7: Post-study Follow-up).

Visit 1 - Screening Period (Day -28 to Day -1):

After signing the informed consent form, Screening assessments will be performed within 28 days of the planned dose to ensure the eligibility of participants. Screening assessments will include:

- Inclusion/Exclusion Criteria
- Demographic data
- Subject number and Investigational Medicinal Product received in MVX0002 study
- Medical history
- Physical examination (full)
- Height, weight and body mass index (BMI)
- Vital signs (supine heart rate, blood pressure, tympanic temperature and respiration rate)
- 12-lead ECG
- Virology (human immunodeficiency virus (HIV), hepatitis B surface antigen (HBsAg) and hepatitis C virus antibody (HCV Ab))
- Laboratory safety tests (biochemistry, haematology)
- Urinalysis
- Urine drugs of abuse including alcohol and cotinine
- Serum pregnancy test
- Follicle Stimulating Hormone Test (Postmenopausal women only)
- Prior and concomitant medication

Visits 2-6 - Treatment Period (Day 1 to Day 85):

Visit 2 (Day 1):

Participants will be admitted to the clinic in the morning of Day 1 and will remain in the unit until the 30 minutes (min) post-dose scheduled assessments. The following procedures will be performed on Day 1.

- COVID-19 Reverse Transcription Polymerase Chain Reaction Test: Pre-dose (can be performed at Visit 1, Day -1 at the discretion of the Principal Investigator (PI))
- Physical examination: Pre-dose (brief) and 30 min (\pm 5 min) post-dose (Symptom-Directed Physical Examination prior to discharge)

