Demographic data will be listed and summarised using the Safety Set. Demographic characteristics will be presented for other analysis sets (Immunogenicity and/or Per Protocol sets) if they differ from the Safety Set.

Safety Data:

All safety data will be listed:

- **AEs:** All AEs occurring up to and including Day 85, including those which occurred prior to dose of Investigational Medicinal Product, will be listed.
- **Physical examinations**
- **Laboratory Safety Test:** biochemistry, haematology, and urinalysis parameters will be listed with any out of normal range values flagged. Laboratory test results which are out of normal range will also be presented separately along with normal reference ranges.
- **Vital Signs:** vital signs parameters will be listed with any out of normal range values flagged. Descriptive statistics (N, n, mean, SD, minimum, median and maximum) of absolute and change from baseline (Day 1 pre-dose) values at each time point will be tabulated.
- **Injection Site Reactions:** a summary of injection site reactions will be produced by visit and category (redness, bruising, induration, itching and pain), including the number and percentage of participants in each category.

Pharmacodynamic Data:

Immunogenicity will be assessed using the Immunogenicity Set and will be repeated for the Per Protocol Set, should the analysis sets differ.

Antibody Response:

Antibody titre responses (IgG concentrations [specific for GBS-NN and GBS-NN2]) will be listed along with the Day 1 and Day 85 results obtained from the MVX0002 study. Antibody response data will be summarised descriptively using number dosed (N), geometric mean and 95% confidence interval (CI) for the geometric mean, , minimum, median, maximum and interquartile range (IQR), by study (MVX0003, MVX0002) and dose level received in the MVX0002 study (placebo/vaccine naïve, 25ug, 50ug) and active doses pooled. Individual and geometric mean plots of antibody concentrations will also be produced by study and dose level received in the MVX0002 study.

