10 INVESTIGATIONAL PLAN

10.1 Overall Study Design and Plan

This is an open label vaccine booster follow-up study. Participants who have received a primary course of GBS-NN/NN2 or placebo in Study MVX0002 will be invited to return to receive a booster dose (or first dose in the case of placebo or vaccine naïve participants) 1 to 5 years after the completion of the primary course of vaccination. All participants will receive a single dose of GBS-NN/NN2 containing 50µg of each fusion protein.

A minimum of 30 and a maximum of 40 female participants will be recruited, comprised of between 20 and 30 participants who had received previous vaccination with GBS-NN/NN2 in the MVX0002 study and up to 10 participants who had received placebo in the MVX0002 study. If an insufficient number (<5) of previous placebo recipient participants return to this study, vaccine naïve participants will be recruited.

The study will include 7 visits (Visit 1: Screening Period, Visits 2-6: Treatment Period and Visit 7: Post-study Follow-up).

The clinical phase is anticipated to take place between June/July 2021 and January/February 2022. The conclusion of the study is defined as last participant last visit.

The study will take place in the Clinical Unit of Simbec-Orion Clinical Pharmacology under full medical and nursing supervision.

A schedule of all study assessments is provided in Table 10.7.1.

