10.7.1.4.1 Adverse Events

AEs and serious adverse events (SAEs) that occurred during the study along with their severity and relationship to study drug will be reported.

An AE is defined as per Statutory Instrument 2004 No. 1031:

Any untoward medical occurrence¹ in a participant to whom a medicinal product has been administered, including occurrences which are not necessarily caused by or related to that product.²

Notes:

¹ Whether subjective complaint or objective finding.

² An AE can therefore be any unfavourable and unintended sign (including an abnormal laboratory finding), symptom, or disease temporarily associated with the use of an IMP, whether or not considered related to the IMP.

An unexpected adverse reaction is defined as:

An adverse reaction, the nature, or severity of which is not consistent with the applicable product information (e.g., IB for an unapproved investigational product or summary of product characteristics (SmPC) for an authorised product).

AEs will be monitored throughout the study from the signature of participant informed consent through to the post-study follow-up visit. All AEs will be recorded, whether considered minor or serious, drug-related, or not.

All abnormal laboratory findings considered to be clinically significant will be recorded as AEs.

Any out of range temperatures, injection site reactions and/or general reactions recorded in the Patient Diary Card for Day 1-Day 7 will be recorded as AEs.

Recording of Adverse Events

All of the following details will be recorded in the participant's eCRF for each AE:

- Full description of AE.
- Date and time of onset.
- Ongoing (Yes/No).
- End Date and time.
- Severity of event to be assessed by an Investigator in accordance with the definitions below.
- Serious Adverse Event (Yes/No) and seriousness criteria (if applicable)
- Relationship to IMP to be assessed by an Investigator in accordance with the definitions below.
- Action taken (if any).
- Outcome and details of any further follow-up.

Grades of Adverse Event Severity

The following grades will be used by an Investigator to describe the severity of AEs.

The following are the only grades, which will be used to describe AE severity. Only 1 severity grade will be used for each AE (e.g., mild - moderate is not acceptable).

| SEVERITY OF THE AE | DEFINITION |
|--------------------|---|

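### The AE listing stops at Day 85 although AEs and SAEs are collected to Day 183, and the general TEAE tables have no stated end date

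*Protocol*

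**What the plan says.** **Collection.** Section 10.7.1.4.1 monitors AEs, and collects SAEs, from consent to the post-study follow-up visit. The synopsis places that visit at Day 183 (±7 days). Footnote 10 of Table 10.7.1 adds a home diary for any AE from Day 85 to Day 183, without limit by type or cause. Section 10.7.1.4.1 also commits to reporting: "AEs and serious adverse events (SAEs) that occurred during the study along with their severity and relationship to study drug will be reported".

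**Listing.** Section 10.9.4.3 opens by saying that all safety data are listed and that what follows is in addition. Its AE paragraph then says: "All AEs occurring up to and including Day 85, including those which occurred prior to dose of IMP, will be listed". The synopsis has the same general promise, without the words that make the items additional, and the same limit: "All AEs occurring up to and including Day 85, including those which occurred prior to dose of Investigational Medicinal Product, will be listed".

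**General TEAE tables.** Section 10.9.4.3 admits to the summary tables "existing conditions that worsen or events that occur during the course of the study after administration of IMP". It gives no last day. Its counting rule for repeat events is: "A participant reporting multiple episodes of a particular AE within a treatment period will only contribute 1 count".

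**Six-month outputs.** The only AE outputs expressly tied to six months are those for "autoimmune diseases and/or clinically relevant medical events related to the vaccination that occur in the 6-month (182 days) follow-up period". This matches the secondary safety endpoint in Section 10.9.2.

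**Objectives.** Section 9.1 sets safety over 12 weeks as primary. Section 9.2 sets the six-month safety profile, compared with vaccine-naïve women, as secondary.

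**The concern.** A listing that stops at Day 85 does not fit a collection period that runs to Day 183, nor the commitment to report AEs and SAEs that occur during the study. The protocol fixes this cut-off itself, in two places, rather than leaving it to the SAP. The window of the general TEAE tables is then left to inference, and the text offers two.

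What is at stake is the six-month comparison. If the general tables stop at Day 85, then apart from autoimmune disease the late comparison uses only events that an investigator, in an open-label study, has judged related to the vaccine. It could not show whether late events of any cause, including serious ones, differ between previously vaccinated and naïve women. If the tables run to Day 183, that comparison is available. The listing would then not support the tables, and the 12-week primary objective would have no general TEAE table cut at its own time point.

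**Working it through.** The protocol states no figure to reproduce. The check compares the windows and does the day arithmetic.

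**Windows side by side**

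| Item | Last day | Limit by cause | Source |
|---|---|---|---|
| AE and SAE collection | Day 183 visit | None | 10.7.1.4.1 |
| Late AE diary | Day 183 | None | Table 10.7.1, footnote 10 |
| AE listing | Day 85 | None | Synopsis; 10.9.4.3 |
| General TEAE tables | Not stated | None | 10.9.4.3 |
| Reactogenicity TEAEs | Day 85 | Reactogenicity only | 10.9.4.3 |
| Autoimmune and/or vaccination-related events | 182 days after dose | Autoimmune or related | 10.9.4.3; 10.9.2 |

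**Which end date do the general TEAE tables have?**

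- *Towards Day 183.* The TEAE definition refers to the course of the study, and Section 10.1 ends the study at the last participant's last visit. The last scheduled visit is Visit 7, on Day 183.
- *Towards Day 85.* The counting rule works within a treatment period. The synopsis gives "Treatment Period (Day 1 to Day 85" and Section 10.1 separates the follow-up visit from it: "Visits 2-6: Treatment Period and Visit 7: Post-study Follow-up".

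**What follows from each reading, for a non-autoimmune event on Day 120 judged unrelated**

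- *Day 183:* it is counted in the TEAE tables but falls outside the specific listing rule.
- *Day 85:* it is in neither the tables nor the specific listing, and it does not qualify for the six-month outputs.

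**Size of the window**

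- Post-dose follow-up: 183 − 1 = 182 days.
- After the listing cut: 183 − 85 = 98 days; 98 / 182 = 53.8%.
- With the ±7-day window for Visit 7: 176 − 85 = 91 to 190 − 85 = 105 days.
- For 30 to 40 women, assuming complete follow-up: 30 × 98 = 2,940 to 40 × 98 = 3,920 person-days. Divided by 365.25, this is 8.0 to 10.7 person-years.

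**Weight of a single late event**

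- Previously vaccinated, 20 to 30 women: 1/30 = 3.3% to 1/20 = 5.0%.
- Naïve, assumed 5 to 10 women (from the ceiling of 10 and the top-up rule below 5): 1/10 = 10% to 1/5 = 20%.

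These are amounts of follow-up and weights per event. The protocol gives no late event rate, so the number of events cannot be derived.

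**The case against.** A reader might infer that late events judged unrelated have no specified output at all. The protocol does not support that, for four reasons.

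1. The TEAE definition has no day limit and no causality limit, and Section 10.1 ends the study at the last visit. Read together, a late unrelated serious event belongs in the overall TEAE summary and in the tables by system organ class, severity and relationship.
2. The treatment-period phrase belongs to a rule for counting repeat episodes; it does not define an output window. The term is also used loosely: Table 10.7.2 places six antibody samples under the treatment period, and footnote 4 of Table 10.7.1 shows that the sixth is taken on Day 183.
3. Where Section 10.9.4.3 wants a Day 85 limit on a summary it says so, as for reactogenicity TEAEs and laboratory descriptive statistics. The general TEAE tables carry no such limit.
4. Section 10.9.4.3 puts its items in addition to listing all safety data, so late events could be listed under that general sentence.

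The first three points stand, and they make Day 183 a well-supported reading of the tables. They do not make it the stated one. The fourth stands only in part. The synopsis lacks the words that make the items additional, and if every AE were already listed to Day 183, the Day 85 phrase would do nothing.

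It can also be said that table cut-offs are SAP matter and that the choice of six-month endpoint is a design decision. Both are fair. The SAP is not at hand and may set the table windows. The Day 85 listing limit, however, is fixed in the protocol, and a SAP that listed AEs to Day 183 would depart from it.

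**Conclusion.** The concern holds as an internal contradiction over the AE listing window, together with an unstated end date for the general TEAE tables. The specific listing rule leaves out 98 of 182 post-dose days (53.8%) of AE collection and conflicts with the general listing promise and the reporting commitment.

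The consequence depends on the reading. With Day 183, the tables and the listing disagree, and no general TEAE table matches the 12-week primary objective. With Day 85, late non-autoimmune events judged unrelated, including serious ones, may appear in no AE listing or table, and the six-month comparison would rest mainly on open-label causality judgements. Either way the wording needs repair.

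Three limits apply. The number of events affected is unknown and may be zero. No direction of bias is claimed, and the 24-hour SAE reporting route is not in question. It is also unclear whether relatedness qualifies autoimmune diseases in the six-month endpoint; here it is taken not to, which is the reading more favourable to the plan.

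**What to change.** Change the Safety Data text in the synopsis and in Section 10.9.4.3 as follows:

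- List all AEs and SAEs from consent to the Day 183 visit.
- Name Day 85 as the cut for the general TEAE tables that serve the 12-week primary objective.
- State that the TEAE and serious-TEAE summary by group (previously vaccinated against placebo/naïve), regardless of causality, is also given to Day 183, with the autoimmune and/or vaccination-related events shown as a subset.

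This works whichever window was intended for the tables. It needs no new data, because late AEs are already entered in the eCRF from the diary and the Visit 7 check. The cost is a wording change in two places and a few extra outputs.
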